4.8.1. Confounding	
4.8.2. Selection bias	
4.9. Statistical analyses	
4.10. Sample size considerations1	1
5. Ethical/data protection issues1	1
6. Plans for communication of study results1	1
7. Amendments and deviations12	2
8. ENCePP Checklist for Study Protocols (Revision 4)	C

1. Milestones

Milestone	Date
Start of data collection	28 April 2020 (including patients from 27 February 2020)
End of data collection	26 May 2020 (or latest available before final report/submission of manuscript)
Final report of study results/submission of manuscript	1 June 2020

2. Background

Case series of hospitalized patients with severe and fatal coronavirus disease 2019 (COVID-19) from China,¹⁻³ Italy,⁴ and the USA^{5,6} have reported a high prevalence (~30%–40%) of hypertension, cardiovascular conditions, and diabetes – conditions often treated with angiotensin converting enzyme inhibitors (ACE-I) and angiotensin II receptor blockers (ARB).⁷ Speculations suggest that use of ACE-I/ARB may increase the risk of developing severe or fatal COVID-19 by upregulating expression of the ACE2 enzyme, which is known to facilitate entry of severe acute respiratory syndrome coronavirus 2 (SARS-CoV-2) into cells.⁸⁻¹² In contrast, ACE-I/ARB use has also been suggested to reduce the risk of acute lung injury in respiratory tract infection in animal studies.¹³ This is supported by a few human studies, which found ACE-I and ARB use to be associated with decreased mortality from bacterial pneumonia,¹⁴⁻¹⁶ while preadmission ACE-I use has been associated with increased mortality in patients hospitalized for viral diseases.¹⁷ A recent Chinese study of 362 patients with hypertension found no increased prevalence of ACE-I/ARB use when comparing survivors with non-survivors of COVID-19.¹⁸ Another Chinese study included 1,128 patients with COVID-19 and found a lower mortality in ACE-I/ARB users compared with non-users. Both studies were limited by potential immortal time bias and confounding by indication as they relied on data on in-hospital use of ACE-I/ARB.^{18,19} The European Medicines Agency, and other major institutions and societies, have called for further research and issued warnings against ACE-I/ARB discontinuation in patients with COVID-19,^{8,20} as drug discontinuation may worsen underlying cardiometabolic conditions.²¹ As ACE-I/ARB are widely used drugs, any association with risk and prognosis may have public health impact. Thus, there is an urgent need to clarify the hypothesis of any increased risk for COVID-19 or worsened prognosis for adverse outcomes of COVID-19 among users of ACE-I/ARB using high-guality population-based data from a uniform tax-supported health care system, while meticulously controlling for potential confounding by indication from coexisting diseases and by using active antihypertensive drug comparators in the analysis.

3. Objectives

The primary aim of the study is to examine the association between ACE-I/ARB use and risk of death in patients with COVID-19. The secondary aim is to examine the association of ACE-I/ARB use with risk of hospital admission, ICU admission, mechanical ventilation, and renal replacement therapy. The third aim is to examine the risk of being diagnosed with COVID-19 among all patients referred to SARS-CoV-2 testing.

4. Methods

4.1. Study design

This nationwide study will include all patients tested for SARS-CoV-2 in Denmark within the source population of all Danish inhabitants.²² The impact of ACE-I/ARB on risk of COVID-19 will be examined using a test-negative case-control design, while the prognosis will be examined in a cohort design of test-positive COVID-19 patients.

4.2. Study period

The study will include patients tested from 27 February 2020 (the date of first identified COVID-19 case in Denmark) to 28 April 2020 (or up to 30 days before manuscript submission) to allow complete follow-up on all included patients.

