4.5. Follow-up

Patients will be followed from the date of the first RT-PCR test for SARS-CoV-2 that turns out to be positive and up to 30 days after that date for all the outcomes. In a sensitivity analysis follow-up for hospitalization will be restricted to 14 days after first positive test.

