4.7. Outcomes

The primary outcome is death within 30 days after positive test for SARS-CoV-2, obtained from the Danish Register of Causes of Deaths.²⁷

Secondary outcomes include hospital admission (in- or acute outpatient stay lasting > 12 hours) at day of or within 30 days after a positive test in patients not already admitted before the date of the test. In addition, outcomes include ICU admission, mechanical ventilation, and renal replacement therapy at day of or within 30 days after positive test for SARS-CoV-2. Secondary outcomes will be obtained from the Danish National Registry, 3rd version (LPR3).²⁴ While the coding has not yet been validated in this LPR3, admission to ICU, mechanical ventilation, and renal replacement therapy are all registered accurately (positive predictive values 96%-100%) in LPR2 as this is also the platform for mandatory reporting to the national database for quality of intensive care.^{28,29}

Finally, in the risk analysis, we identified patients with positive tests among all patients tested for SARS-CoV-2.

[figure not shown]

Figure illustrating the endpoints in the COVID-19 risk analysis and the endpoints in the COVID-19 prognosis analysis.

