4.9. Statistical analyses

In the analyses of prognosis, patients will be followed from day of SARS-CoV-2 positive test result and until date of hospital admission, ICU admission (in analysis of ICU admission), date of death, end of follow-up or for up to 30 days.

Patient characteristics will be tabulated according to each exposure group.

Descriptive analyses will explore the timing of outcomes one month prior to and three months after the first positive test for SARS-CoV-2. In case of a substantial fraction of outcomes having occurred in the days leading up to a positive test, a post-hoc analysis with a larger follow up windows (pre- and post-test) will be conducted.

For each exposure group, we will estimate the 30-day PS-weighted cumulative incidence (risk) of of death, and of each of the non-fatal events (hospital admission, ICU admission, ICU+MV, ICU+inotropes/vasopressors, RRT) accounting for competing risk by death. All 95% confidence intervals will be computed using bootstrapping. The risk of each outcome within 30 days will be computed with 95% CI.

Propensity scores for each comparison (e.g. current ACE-I/ARB use vs. current CCB use) will be computed using logistic regression including all the potential confounders as described above. All other exposures (anti-hypertensive drugs) will be included in the PS-model. The propensity score weighted (SMRW=ATT) cumulative incidence (risk) of each outcome will be plotted and estimated with 95% CI estimated by bootstrapping. The adjusted (PS weighted) risk difference will be computed for the 0-30 period.

The 30-day risk will be compared using PS weighted log binomial regression to estimate risk ratio for death, hospital admission, ICU admission, ICU+MV, RRT, and ICU+inotropes/vasopressors.

Subgroup analysis will be conducted to address effect modifiers including age group (=<65, >65 years) and in patients with assumed uncomplicated hypertension as the primary indication for treatment, defined as patients without any history of diabetes, renal disease, angina pectoris, myocardial infarction, or heart failure. We will also stratify by ABO blood type, if available, because blood type is suggested to be associated with ACE2.³⁰

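### The stated dates do not guarantee the complete 30-day follow-up claimed in section 4.2: inclusion to 28 April needs data to 28 May, but the default data end is 26 May, and the alternative rule counts back from submission instead of the data cut

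*Protocol*

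**What the plan says.** The protocol fixes the relevant dates in several places.

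- Section 4.2 (Study period) includes patients tested from 27 February 2020 "to 28 April 2020 (or up to 30 days before manuscript submission) to allow complete follow-up on all included patients".
- Section 4.5 (Follow-up) follows patients from the first positive test "up to 30 days after that date for all the outcomes".
- Section 4.7 (Outcomes): "The primary outcome is death within 30 days after positive test for SARS-CoV-2".
- Section 1 (Milestones) gives the end of data collection as "26 May 2020 (or latest available before final report/submission of manuscript") and plans the final report or submission for 1 June 2020.
- Section 4.9 (Statistical analyses): "The 30-day risk will be compared using PS weighted log binomial regression to estimate risk ratio for death" and for the other outcomes. It also plans weighted cumulative incidences with death as a competing risk, and a descriptive look at the timing of outcomes "one month prior to and three months after the first positive test for SARS-CoV-2".

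The only shorter window is in section 4.5: "In a sensitivity analysis follow-up for hospitalization will be restricted to 14 days after first positive test". It does not apply to death.

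**The concern.** Section 4.2 gives complete follow-up as the reason for its cut-off. Whether follow-up is complete depends on how far the register data run, and no section ties the last inclusion date to the data cut. The fixed inclusion date and the fixed data end are less than 30 days apart. The alternative inclusion rule is anchored to manuscript submission, which says nothing about how far the data run.

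The main risk is to the risk ratio for the primary outcome. A log-binomial model of 30-day death takes a yes/no value for each patient and cannot represent someone observed for 24 or 28 days. If that patient dies on day 29 and the data have already ended, the death is recorded as survival. The patients affected are those tested last, and section 4.8.2 says that testing and admission criteria changed over the period.

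**Working it through.** **Inputs.** Last inclusion date 28 April 2020, or submission minus 30 days (section 4.2). Follow-up 30 days (sections 4.5 and 4.7). Default data end 26 May 2020 and submission 1 June 2020 (section 1). First inclusion date 27 February 2020 (section 4.2).

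**Step 1: the claim on the fixed dates.** Completeness requires last test date + 30 days ≤ data end.
- 28 April + 30 days = 28 May, which is 2 days after 26 May. The claim is not reproduced.
- Counting the test day as day 1, the 30th day is 28 April + 29 days = 27 May, still after 26 May.
- Turned round, 26 May − 30 days = 26 April is the last test date with full follow-up.

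**Step 2: the submission-based rule.** 1 June − 30 days = 2 May. Follow-up at each data cut:

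| Test date | Days available at 26 May | Days available at 1 June |
|---|---|---|
| 26 April | 30 | 36 |
| 27 April | 29 | 35 |
| 28 April | 28 | 34 |
| 29 April | 27 | 33 |
| 30 April | 26 | 32 |
| 1 May | 25 | 31 |
| 2 May | 24 | 30 |

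If inclusion is taken to its limit, this rule falls short by exactly the gap between data cut and submission. The gap is zero only if data run to the day of submission. On the milestone dates it is 6 days.

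**Step 3: rough size.** Two simplifying assumptions, neither from the protocol: tests spread evenly over the inclusion dates, and deaths spread evenly over the 30 days.
- Default dates: 27 February to 28 April is 62 test dates, so 62 × 30 = 1,860 units of follow-up. Missing: 1 + 2 = 3. Share 3/1,860 = 0.16%.
- Submission rule with a 26 May cut: 66 test dates, 66 × 30 = 1,980 units. Missing: 1 + 2 + 3 + 4 + 5 + 6 = 21. Share 21/1,980 = 1.1%.
- To give a scale, apply these shares to the 364 deaths in section 4.10 (counted at 20 April): 364 × 3/1,860 ≈ 0.6 deaths and 364 × 21/1,980 ≈ 4 deaths, over all exposure groups together.

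**Step 4: registration delay.** The protocol gives no figure. If events are complete only up to L days before the cut, the last fully observed test date for a 26 May cut becomes 26 April − L days.

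**Step 5: the three-month description.** 27 February + 3 months = 27 May. At 26 May even the first possible patient has only 89 days. With data to 1 June, only tests up to 1 March reach three months: 4 of the 62 test dates.

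**The case against.** The strongest reply is the wording in section 1 that allows the latest available data before submission. 28 May falls before 1 June, so an update between 28 May and 1 June makes the 28 April cut-off complete within the protocol's own text. A reader might infer from the fixed dates that a shortfall is certain, and the documents do not support that. The 24-day figure also pairs the flexible option of section 4.2 with the fixed option of section 1. The two flexible options may have been meant to move together, and the inclusion rule is a ceiling. All of this stands. What remains is that the later data are optional, and that even with them the submission rule is complete only when the data cut is the day of submission.

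A reader might also infer that every 30-day estimate is biased. Section 4.9 lists end of follow-up among the exits, so the cumulative incidences, and risk differences taken from them, can censor patients at the cut. The problem lies mainly with the log-binomial risk ratios.

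Unequal bias between exposure groups is another tempting inference. It is possible but not shown. Calendar time is in the propensity score, although only as before or after lockdown, and an analysis stratified by calendar time is planned.

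Nor can the three-month window be called impossible: with later data a few early patients would complete it. It is exploratory, and no effect estimate depends on it.

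Finally, the test-negative analysis needs no follow-up, so an earlier cut-off there would discard tests for no gain.

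**Conclusion.** The point holds as a mismatch of dates. Section 4.2 claims a property that its own cut-off and the default data end do not deliver: tests on 27 and 28 April lack 1 and 2 days. The alternative rule has the wrong anchor and can leave six test dates short by 1 to 6 days.

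The expected numerical effect is small: about 0.16% of follow-up on the default dates and about 1.1% in the less favourable combination, both resting on even spread of tests and deaths. A registration delay would add to this, but its length is not in the documents and no size is claimed for it. The bias would act on the log-binomial risk ratios by counting late deaths as survival. The case for correcting it is that the claim can be made true by wording alone. The three-month description is a secondary point: almost no patient can have that window observed by 1 June.

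**What to change.** - For the prognosis cohort, define the last eligible positive-test date as the register data cut minus 30 days, less any known registration delay. Before any such delay is deducted, that is 26 April for a 26 May cut; to keep 28 April, require data through at least 28 May.
- Remove the link to manuscript submission from section 4.2 and make sections 1 and 4.2 refer to the same data cut.
- State that the test-negative analysis keeps all tests in the study period.
- In section 4.9, limit the three-month description to the follow-up available, or censor it there.

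The cost is date wording, plus either a few days of inclusions lost from the prognosis cohort or an extraction a few days later.

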4.3. Data sources

The study will include nationwide secondary data from The Danish COVID-19 cohort, which includes linked individual-level data on all Danish inhabitants tested for SARS-CoV-2 from The Danish Microbiology Database (MIBA),²³ The Danish National Registry of Patients (DNRP),²⁴ The Danish Civil Registration System (CRS),²⁵ The National Prescription database (NPD),²⁶ and The Danish Cause of Death Registry.²⁷

5

4.4. Study population

The source population is all Danish citizens (popuation~5.8 million).²² The study population for risk analysis (the test-negative case-control analysis) will be all patients tested for SARS-CoV-2, while the prognosis analysis (cohort analysis) will only include patients tested positive SARS-CoV-2, *i.e.*, patients with COVID-19.

4.5. Follow-up

Patients will be followed from the date of the first RT-PCR test for SARS-CoV-2 that turns out to be positive and up to 30 days after that date for all the outcomes. In a sensitivity analysis follow-up for hospitalization will be restricted to 14 days after first positive test.

4.6. Exposure

The study is designed to address acute effects of current use of ACE-I/ARB, and we do not expect any cumulated effect of long-term ACE-I/ARB use. The half-life of ACE-I/ARB ranges from 1 to 24 hours.

The exposure will be defined by filled prescriptions for ACE-I/ARB and other antihypertensive drugs within 90 days before test for SARS-CoV-2. Data on prescriptions are obtained from the Danish Prescription Registry, which include complete and valid information on all filled prescriptions at community pharmacies in Denmark since 1995.²⁶ Data include, among others, date of dispensing, Anatomical Therapeutic Chemical (ATC) code, and drug quantity.

The main exposures will be:

- Current use (prescription filled within prior 90 days before test) of ACE-I/ARBs, compared with
 - Current use (prescription within 90 days) of calcium channel blockers (CCB), a cardiovascular drug used for similar medical indications as ACE-I and ARB, to assess if any observed association with outcomes is specific to ACE-I/ARB exposure.

• No use of ACE-I or ARB (prescription >365 days or never)

Secondary exposures will be:

- Former versus no use of ACE-I or ARB (former use defined as prescription 91-365 days before test)
- Current ACE-I/ARB use compared with:
 - Current use of thiazides (prescription within 90 days)
 - Current use of beta-blockers (prescription within 90 days)

As an additional analysis, ACE-I and ARB will be analyzed separately if the number of exposed are sufficient.

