4.8.3. Information bias

There may be some misclassification of the exposure, which will be addressed in a sensitivity analysis as described. Any misclassification is not expected to be associated with the outcomes of interest (non-differential misclassification), and any information bias are therefore expected to be towards the null.

As outcomes are accurately recorded, any misclassification is expected to be minor and not associated with the exposure.

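### Counting the 90-day exposure window back from the test moves some ACE-I/ARB users already in hospital to former use, while non-users in hospital all stay in the comparator

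*Protocol*

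**What the plan says.** Protocol 4.6 defines exposure from dispensing data: "The exposure will be defined by filled prescriptions for ACE-I/ARB and other antihypertensive drugs within 90 days before test for SARS-CoV-2". The source is a registry described as holding "complete and valid information on all filled prescriptions at community pharmacies in Denmark since 1995". Section 4.3 names no source for ACE-I/ARB given in hospital.

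The same section sets three groups by time since the last fill. Current use is a fill in the prior 90 days. Former use is separate ("former use defined as prescription 91-365 days before test"). The comparator in one of the two main contrasts is "No use of ACE-I or ARB (prescription >365 days or never". The other main comparator has the same 90-day rule as ACE-I/ARB: "Current use (prescription within 90 days) of calcium channel blockers (CCB".

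Protocol 4.7 foresees patients who are in hospital when tested, but uses this only to restrict the hospital-admission outcome, which is assessed "in patients not already admitted before the date of the test". For death there is no such restriction: "The primary outcome is death within 30 days after positive test for SARS-CoV-2".

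Protocol 4.8.3 says exposure misclassification will be examined in a sensitivity analysis and expects it to be harmless in direction: "Any misclassification is not expected to be associated with the outcomes of interest (non-differential misclassification", hence towards the null. The sensitivity analysis, in 4.9, widens the fill window to 120 days, again counted from the test. The covariate list in the code table does not include being an inpatient at the test.

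**The concern.** For a patient already in hospital, each day between admission and test lengthens the time since the last community fill, whether or not treatment continues. An ongoing user admitted 14 days before the test, with a last fill 80 days before admission, has a last fill 80 + 14 = 94 days before the test. That patient becomes a former user and leaves the main contrast. A never-user in hospital for the same 14 days stays in the non-use group, because that group needs no recent fill.

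The loss is therefore one-sided and depends on being an inpatient. If inpatients have higher 30-day mortality, the remaining current-use group has too few high-risk patients and its risk looks too low against non-use. The displaced patients raise the risk in the former-use group, so the secondary former versus non-use contrast moves the other way. A pattern of current use looking protective and former use looking harmful could be misread as an effect of stopping treatment, a worry that the background section itself raises.

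**Working it through.** The protocol gives no figure for this error, so there is none to reproduce. The RR of 1.2 in 4.10 serves only as a yardstick.

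**Inputs from the protocol.** Window of 90 days back from the test; former use 91 to 365 days; sensitivity window 120 days; assumed mortality in the unexposed 4%; observed deaths among positives 4.8%.

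**Inputs the protocol does not give, assumed here.** Refill interval R = 90 or 100 days; time since last fill at admission uniform over 0 to R; no community fills during the stay; pre-test stay L = 3 to 60 days; inpatient share of positives h = 2% to 20%; inpatient mortality k = 3 or 5 times that of others; true RR = 1.

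**Step 1: share of ongoing users lost among inpatients.** With R = 90, the share is L/90. Nobody outside hospital is lost. With R = 100, it is (10 + L)/100 among inpatients and 10% among others.

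**Step 2: apparent RR.** With l the share lost and R = 90,

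RR = {[h(1−l)k + (1−h)] / [h(1−l) + (1−h)]} / [hk + (1−h)].

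Example with h = 10%, k = 5, L = 14: l = 14/90 = 0.156 and h(1−l) = 0.0844. The first ratio is (0.422 + 0.9)/0.984 = 1.343; the divisor is 0.5 + 0.9 = 1.4; RR = 0.959.

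| Stay before test | Inpatient users lost (R = 90) | RR: h 2%, k 3 | RR: h 10%, k 3 | RR: h 10%, k 5 | RR: h 20%, k 5 |
|---|---|---|---|---|---|
| 3 days | 3% | 0.999 | 0.995 | 0.991 | 0.988 |
| 7 days | 8% | 0.997 | 0.988 | 0.980 | 0.972 |
| 14 days | 16% | 0.994 | 0.976 | 0.959 | 0.943 |
| 28 days | 31% | 0.988 | 0.952 | 0.917 | 0.882 |
| 60 days | 67% | 0.975 | 0.893 | 0.816 | 0.726 |

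With R = 100 the RRs are the same, because the retained share of inpatients relative to others is again (90 − L)/90.

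**Step 3: a second set of mortality inputs.** With 20% mortality in inpatients, 3% in others and h = 10%, overall mortality is 0.1 × 20% + 0.9 × 3% = 4.7%, close to the observed 4.8%. The RR is then 0.97, 0.95 and 0.89 for stays of 7, 14 and 30 days.

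**Step 4: what the 120-day window recovers.** The longest possible gap at the test is L + R. It stays within 120 days if L ≤ 30 (R = 90) or L ≤ 20 (R = 100). Longer stays are not fully recovered.

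**Step 5: counting from admission.** With the window ending at admission, inpatients and others are classified by the same rule, the lost shares are equal, and the apparent RR in this model is 1.00.

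**The case against.** The strongest reply is that the protocol already has a check. Section 4.8.3 points to a sensitivity analysis, and the 120-day window recovers the 94-day patient above and every loss for stays up to 20 to 30 days. This stands, with limits. It leaves the primary estimate as it is, is also counted from the test, and misses longer stays. It also reclassifies people outside hospital with late refills, so a changed result could not be traced to inpatients.

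Second, a reader might infer that inpatients as a group drop out of the ACE-I/ARB arm. They do not: in the 90-day refill model 92% of inpatient users remain after 7 days and 84% after 14.

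Third, the inputs are unsourced. The protocol gives no inpatient share, length of stay, inpatient mortality or refill interval. That inpatients fill no community prescriptions is an inference from the data source, and higher inpatient mortality is plausible but not stated. Extreme inputs can also clash with the protocol's own data: 20% inpatients with 20% mortality and 3% in others imply 0.2 × 20% + 0.8 × 3% = 6.4% deaths, against 4.8% observed. The model is unadjusted as well, and weighting on comorbidity may remove part of the imbalance. All this limits what can be said about size, but not the mechanism.

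Fourth, the CCB contrast has the same rule in both arms and is largely protected. This stands; the point concerns the non-use contrasts.

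Fifth, a reader might infer that the test-negative odds ratio is distorted too. Nothing in the protocol shows how inpatients divide between positives and negatives, so neither direction nor size can be claimed.

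Last, the study targets acute effects of current use, and counting from admission could label as current a patient whose last fill was 80 + 30 = 110 days before the test. This is a real trade-off, but in-hospital use is unobserved under either rule.

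**Conclusion.** The point holds for current use versus non-use and former use versus non-use. The protocol keeps patients already in hospital in the death analysis, judges their exposure by community fills counted from the test, and does not list inpatient status as a covariate. If inpatients die more often and do not fill community prescriptions during the stay, the error is related to the outcome. It then pushes the first contrast towards apparent protection and the second towards apparent harm. The expectation in 4.8.3 does not cover this case.

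The size cannot be determined from the documents. Under the assumptions above, the apparent RR is about 0.94 to 1.00 for pre-test stays of 3 to 14 days, 0.88 to 0.99 for 28 days and 0.73 to 0.98 for 60 days. Against a target RR of 1.2 this is small for short stays and material only when stays are long and the inpatient share is sizeable. A reader might infer that the primary result will be seriously biased; the documents do not support that. They support a cheap correction made before the data are analysed.

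**What to change.** In 4.6, for patients admitted before the test date, count the exposure windows (90 days, 91 to 365 days, and the 120-day sensitivity window) and the 90-day co-medication look-backs back from the admission date of that stay. Keep the test date for everyone else. At minimum, pre-specify this as a sensitivity analysis for the non-use contrasts. In 4.8.3, limit the statement on non-differential misclassification to patients not in hospital at the test.

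The cost is a wording change and one derived date. The restriction of the admission outcome in 4.7 already requires knowing who was admitted before the test, from the same linked patient registry. The downside is that for long stays the classification reflects use at admission, so stopping in hospital is not seen; it is not seen under the present rule either.

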The risk of COVID-19 (a positive test for SARS-CoV-2) will be analyzed using a testnegative case-control design among all patients tested. All covariates will be tabulated for patients with a positive test and negative test for SARS-CoV-2. The odds ratio for current ACE-I/ARB use vs. non-use and CCB use, respectively, will be estimated using two separate logistic regression models adjusted for all covariates, see Appendix.

In a sensitivity analysis, we will explore the robustness of our findings by repeating the analyses in patients who filled a prescription within 120 days before a positive test.

Finally, we will do a sensitivity analysis stratified by calendar time to address changes in testing and hospitalization strategy.

10

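### Former use starts at day 91 with no gap after current use, so an unquantified share of the former users in a secondary contrast may still be on treatment

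*Protocol*

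**What the plan says.** Section 4.6 of the protocol divides ACE-I/ARB exposure by time since fill:

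- Current: "Current use (prescription filled within prior 90 days before test) of ACE-I/ARBs, compared with" the comparators.
- Former, as a secondary exposure: "Former versus no use of ACE-I or ARB (former use defined as prescription 91-365 days before test".
- None: "No use of ACE-I or ARB (prescription >365 days or never".

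The same section says "The study is designed to address acute effects of current use of ACE-I/ARB", expects no cumulative effect, and gives a half-life of 1 to 24 hours. On the source data it says "Data include, among others, date of dispensing, Anatomical Therapeutic Chemical (ATC) code, and drug quantity". Section 4.8.3 states "There may be some misclassification of the exposure, which will be addressed in a sensitivity analysis as described" and expects any resulting bias to be towards the null. Section 4.9 describes that sensitivity analysis as "repeating the analyses in patients who filled a prescription within 120 days before a positive test". It does not say what happens to the former-use window when the current-use window is widened.

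**The concern.** For an acute effect of a short half-life drug, a former-use group is informative only if its members have stopped. With no gap, and with status set by fill date alone, the group takes in two kinds of patient at day 91: those who have stopped, and those who continue but have supply beyond 90 days or are slightly late refilling. Ongoing users are likely to far outnumber those who stop in a year, so even short refill delays could make up a noticeable part of the former group.

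If so, a real current-use effect would partly show up in former users as well. A reader comparing the current-use and former-use estimates could then take a drug effect for confounding by indication. The general expectation of bias towards the null in section 4.8.3 does not cover this. If true former users carry no excess risk, still-treated patients in that group move its estimate away from the null.

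**Working it through.** The protocol states no figure for this contrast, so there is none to reproduce.

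**1. Overlap of the windows (protocol figures only).**
- Former-use window: 365 − 91 + 1 = 275 days.
- Days that are former in section 4.6 and exposed in the 120-day analysis: 120 − 91 + 1 = 30.
- Share of the window: 30/275 = 10.9%.

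**2. Share of the former group still holding supply (assumed inputs).** The protocol gives no pack size, days' supply, refill interval or stopping rate. Assume a refill interval of S days, each fill lasting S days, and d stoppers per year per 100 ongoing users. Last fills are taken as uniform over 0 to S days in ongoing users and over the past year in stoppers. Per 100 ongoing users:
- ongoing users falling in the former window: 100 × (S − 90)/S
- stoppers in the window: d × 275/365
- stoppers in the window still supplied: d × (S − 90)/365
- share still supplied = (first + third)/(first + second)

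Worked case, S = 100 and d = 10: first = 10.0, second = 7.5, third = 0.27, so the share is 10.27/17.53 = 59%.

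| S (days) | d = 30 | d = 20 | d = 10 | d = 5 |
|---|---|---|---|---|
| 90 | 0% | 0% | 0% | 0% |
| 95 | 20% | 27% | 42% | 59% |
| 100 | 33% | 42% | 59% | 74% |
| 120 | 58% | 67% | 79% | 88% |

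**3. Effect on the estimate.** Suppose a share f of the former group is truly current, true former users have RR 1.0, and baseline risks are equal. The expected former-versus-no-use RR is then f × RR(current) + (1 − f) × 1.0. With the RR of 1.2 from section 4.10:
- f = 0.109: 1.02
- f = 0.5: 1.10
- f = 0.7: 1.14

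**4. Effect of starting at day 121.** The window becomes 275 − 30 = 245 days. In the model of step 2, with S at most 120, nobody still supplied remains in it. The former group shrinks by 10.9% at S = 90, by 38%-76% at S = 100 and by 58%-88% at S = 120 (d = 30 to 5). Among stoppers the loss is 30/275 = 10.9% throughout. Any larger reduction comes from ongoing users leaving the group.

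**The case against.** A reader might infer that the former group consists largely of people still taking the drug. The documents do not support that. They give no supply or refill data, and the modelled share runs from nil to a majority depending on assumptions alone.

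A reader might also take the 120-day analysis as an admission that patients at days 91-120 are exposed, and hence as a contradiction. It is not one. It tests the robustness of a cut-off, and any such test moves some patients between categories. Nor can one say that this analysis fails to help. Repeating the analyses at 120 days could be read as moving former use to 121-365 days, although the protocol does not say so.

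The purpose of the contrast is inferred as well. Section 4.6 gives the specificity question to the CCB comparator. Section 4.8.1 gives confounding by indication to propensity scores, active comparators and restriction. Finally, a definition based on fill date is transparent and prespecified. One built on dispensed quantity would need an assumed daily intake and would bring its own misclassification.

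All of this stands, and it limits the size and rank of the point. It does not supply a reason for having no gap between current and former use.

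**Conclusion.** The point holds as a weakness in the definition of one secondary contrast. Former use begins directly after current use, and the plan's own alternative window treats the first 30 of its 275 days as exposed. An unquantified share of former users may therefore still be treated, which would pull the former-versus-no-use estimate towards the current-use effect. Only the 10.9% overlap in days follows from the protocol. The patient shares rest on assumed refill and stopping rates, and the RR shifts also on a null effect in true former users and equal baseline risks.

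The definition of former use does not affect the main contrasts. Current versus no use leaves out last fills on days 91-365, and current versus CCB use is not built from the former-use category.

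**What to change.** In section 4.6, define former use as a last fill 121-365 days before the test, with days 91-120 left out of this contrast as a gap. The boundary is one the plan already uses, and it removes the days most likely to hold late refillers. At the least, section 4.9 should state that the former-versus-no-use contrast will also be reported with the 121-365 window alongside the 120-day sensitivity analysis.

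The cost is one line of text, one recoded variable and a somewhat smaller former-user group. The window loses 30 of 275 days, which is 10.9% of the group if last fills are evenly spread. The loss is larger if late refillers are common, but it then falls mainly on patients who do not belong in the group. Ongoing users whose last fill was more than 120 days ago would still be counted as former.
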